6.3. Smoking

Subjects will not be permitted to use tobacco- or nicotine-containing products within 3 months prior to check-in until the follow-up visit.

6.4. Exercise

Subjects are required to refrain from strenuous exercise from 7 days before check-in until the follow-up visit (Day 29±2 days) and will otherwise maintain their normal level of physical activity during this time (ie, will not begin a new exercise program nor participate in any unusually strenuous physical exertion).

6.5. Blood Donation

Subjects are required to refrain from donation of blood from 3 months prior to screening, plasma from 2 weeks prior to screening, and platelets from 6 weeks prior to screening until 3 months after the follow-up visit.

7. STUDY ASSESSMENTS AND PROCEDURES

Every effort will be made to schedule and perform the procedures as closely as possible to the nominal time, giving considerations to appropriate posture conditions, practical restrictions, and the other procedures to be performed at the same timepoint.

The highest priority procedures will be performed closest to the nominal time. The order of priority for scheduling procedures around a timepoint is (in descending order of priority):

- dosing
- continuous ECG extraction window
- pharmacokinetic blood samples
- safety assessments
- any other procedures.

This study includes a screening period (Day -28 to Day -3 [or Day -5 depending on the clinical site's requirement for COVID-19 testing]), a treatment period (Days -2 [or Day -4] to 19), and a follow-up period (Day 29 ±2 days).

The defined abnormal vital sign measurements (Exclusion Criteria #4) at check-in (Day -2 or Day -4 depending on the clinical site's requirement for COVID-19 testing) or baseline (Day -1 predose) will only be considered exclusionary if judged applicable by the investigator. For confirmation of enrollment eligibility based on pulse rate, the pulse rate assessed by vital signs, rather than the 12-lead ECG, will be used. For all subjects, the screening, check-in, or baseline blood pressure, pulse rate, and respiratory rate may be repeated after 5 to 10 minutes if the initial reading is believed to be atypical for the subject.

7.1. General Assessments

7.1.1. Demographics

Demographic data collection including sex, age, race, and ethnicity will be collected in order to study their possible association with subject safety and treatment effectiveness.

7.1.2. Medical History

At the timepoint specified in [Appendix 6](#), the investigator or designee will collect a complete medical and surgical history. Medical history will include information on the subject's concurrent medical conditions and any events occurring prior to the first dose of study treatment. All findings will be recorded on the medical history eCRF.

7.2. Electrocardiography Assessments

7.2.1. Continuous 12-lead Electrocardiogram Recording

Continuous 12-lead digital ECG recording will be performed as specified in [Appendix 6](#). All ECG data will be collected using a Holter (or Mortara Surveyor) ECG continuous 12-lead digital recorder. The 12-lead Holter (or Mortara Surveyor) ECG equipment will be supplied and supported by ERT (eResearch Technology Inc., Philadelphia, PA). The continuous 12-lead digital ECG data will be stored onto SD memory cards.

The ECGs to be used in the analyses will be selected by predetermined timepoints as defined in [Appendix 6](#) and will be read centrally by ERT (eResearch Technology Inc., Philadelphia, PA). The following principles will be followed in ERT's core laboratory:

- ECG analysts are blinded to the subject, visit, and treatment allocation.
- Baseline and on-treatment ECGs for a particular subject will be over-read on the same lead and will be analyzed by the same reader.

The primary analysis lead is lead II. If lead II is not analyzable, then the primary lead of analysis will be changed to another lead for the entire subject data set.

The 12-lead ECGs will be extracted in up to 10 replicates at the predefined timepoints and subjects will be inactive and in a supine position for at least 10 minutes prior to and 5 minutes after each nominal time.

7.2.1.1. *TQT Plus Extraction Technique*

Ten 14-second digital 12-lead ECG tracings will be extracted from the continuous Holter (or Mortara Surveyor) recordings using the 'TQT Plus method', a computer-assisted and statistical process utilized by ERT. The method enables extraction of ECGs with the lowest HR variability and noise within the protocol-specified extraction time window (eg, the HR and QT changes from beat-to-beat in the range of <10%). At each protocol-specified timepoint, 10 ECG replicates will be extracted from a 5-minute "ECG window" (typically,

the last 5 minutes of the 15-minute period when the subject is maintained in a supine, quiet position).

7.2.1.2. *Expert Precision QT Analysis*

Expert precision QT analysis will be performed on all analyzable (non-artifact) beats in the 10 ECG replicates. Statistical quality control procedures are used to review and assess all beats and identify “high” and “low” confidence beats using several criteria, including:

- QT or QTc values exceeding or below certain thresholds (biologically unlikely).
- RR values exceeding or below certain thresholds (biologically unlikely).
- Rapid changes in QT, QTc, or RR from beat-to-beat.

Measurements of all primary ECG parameters (QT, QTc, RR) in all recorded beats of all replicates that are deemed “high confidence” will be performed using COMPAS software. All low-confidence beats will be reviewed manually and adjudicated using pass-fail criteria. The final QC assessment will be performed by a cardiologist. The beats found acceptable by manual review will be included in the analysis. The median QT, QTc, and RR values from each extracted replicate will be calculated, and then the mean of all available medians from a nominal timepoint will be used as the subject’s reportable value at that timepoint.

Categorical T-wave morphology analysis and the measurement of PR and QRS interval of the ECG (QRS) intervals will be performed manually in 3 of the 10 ECG replicates at each timepoint. Each fiducial point (onset of P-wave, onset of Q-wave, offset of S-wave, and offset of T-wave) will be electronically marked.

For T-wave morphology and U-wave presence, treatment-emergent changes will be assessed (ie, changes not present at baseline). For each category of T-wave morphology and U-waves, the category will be deemed as present if observed in any replicate at the timepoint. For baseline, the category will be deemed as present if observed in any replicate from all timepoints that constitute baseline.

7.2.2. *Safety 12-lead Electrocardiogram*

Resting 12-lead ECGs will be recorded after the subject has been supine and at rest for at least 5 minutes at the times indicated in the Schedule of Assessments in [Appendix 6](#). Single 12-lead ECGs will be repeated twice, and an average taken of the 3 readings, if either of the following criteria applies:

- QT interval corrected for HR using Fridericia’s method (QTcF) is >500 ms
- QTcF change from the baseline (predose) is >60 ms.

Additional 12-lead ECGs may be performed at other times if judged to be clinically appropriate or if the ongoing review of the data suggests a more detailed assessment of ECGs is required. The investigator (or designee) will perform a clinical assessment of each 12-lead ECG.

7.2.3. Cardiac Telemetry Monitoring

Subjects will be monitored via cardiac telemetry from approximately 1 hour prior to dose administration and until approximately 12 hours postdose on Days 1, 2, 3, and 7 (up-titration days; as described in [Appendix 6](#)). Based on the emerging safety data from the study, the duration of the telemetry may be extended if necessary.

The start and stop date and time of the telemetry monitoring will be recorded in the eCRFs. Clinically significant abnormalities noted from telemetry monitoring will be confirmed by 12-lead ECG if necessary, then after confirming, the abnormalities will be reported as AEs in the eCRF.

7.3. Pharmacokinetic Assessments

7.3.1. Pharmacokinetic Blood Sample Collection and Processing

Blood samples (approximately 1×4 mL for CBP-307 and moxifloxacin assays) will be collected by venipuncture or cannulation at the times indicated in the Schedule of Assessments in [Appendix 6](#). Procedures for collection, processing, and shipping of PK blood samples will be detailed in a separate document.

7.3.2. Analytical Methodology

Plasma concentrations of CBP-307 and moxifloxacin will be determined using a validated analytical procedure. Specifics of the analytical method will be provided in a separate document.

7.4. Safety and Tolerability Assessments

7.4.1. Adverse Events

Adverse event definitions, assignment of severity and causality, and procedures for reporting SAEs are detailed in [Appendix 1](#).

The condition of each subject will be monitored from the time of signing the ICF until the follow-up visit. Subjects will be observed for any signs or symptoms and asked about their condition by open questioning, such as “How have you been feeling since you were last asked?”, at least once each day while resident at the study site and each study visit. Subjects will also be encouraged to spontaneously report AEs occurring at any other time during the study.

All nonserious AEs, whether reported by the subject voluntarily or upon questioning, or noted on physical examination, will be recorded from initiation of placebo administration to all subjects (Day -1) until study completion. If AEs that occur in the screening prior to placebo administration to all subjects (Day -1) are considered to be related to the study procedure, they should be also collected. Serious AEs will be recorded from the time the subject signs the ICF until study completion. The nature, time of onset, duration, and severity will be documented, together with an investigator’s (or designee’s) opinion of the relationship to study treatment.

Adverse events recorded during the course of the study will be followed up, where possible, to resolution or until the unresolved AEs are judged by the investigator (or designee) to have stabilized. This will be completed at the investigator's (or designee's) discretion.

7.4.2. Clinical Laboratory Evaluations

Blood and urine samples will be collected for clinical laboratory evaluations at the times indicated in the Schedule of Assessments in [Appendix 6](#). Clinical laboratory evaluations are listed in [Appendix 2](#).

A serum qualitative pregnancy or urine test (females only) and follicle-stimulating hormone test (postmenopausal females only) will be performed at the timepoints specified in [Appendix 6](#). A positive urine pregnancy test will be confirmed with a serum pregnancy test. All pregnancies should be reported as specified in [Appendix 1](#).

Additional clinical laboratory evaluations will be performed at other times if judged to be clinically appropriate or if the ongoing review of the data suggests a more detailed assessment of clinical laboratory safety evaluations is required. At the discretion of the investigator, clinically significant clinical laboratory assessments may be confirmed by repeat sampling. If the clinical significance is confirmed, subjects will be excluded from participation or, if already included, will be followed until normalization of the test result or for as long as the investigator considers necessary.

Subjects will be asked to provide urine samples for drugs of abuse screen and cotinine test, and will undergo an alcohol breath test at the times indicated in the Schedule of Assessments in [Appendix 6](#). For all female subjects, a pregnancy test will be performed at the times indicated in the Schedule of Assessments in [Appendix 6](#).

An investigator (or designee) will perform a clinical assessment of all clinical laboratory data.

7.4.3. Vital Signs

Supine blood pressure, supine pulse rate, respiratory rate, and tympanic temperature will be assessed at the times indicated in the Schedule of Assessments in [Appendix 6](#). Vital signs may also be performed at other times if judged to be clinically appropriate or if the ongoing review of the data suggests a more detailed assessment of vital signs is required.

All measurements will be performed singly. For all subjects, the screening, check-in, or baseline blood pressure, pulse rate, and respiratory rate may be repeated after 5 to 10 minutes if the initial reading is believed to be atypical for the subject.

Subjects must be supine for at least 5 minutes before blood pressure and pulse rate measurements.

7.4.4. Physical Examination

A full physical examination will be performed at the timepoints specified in the Schedule of Assessments in [Appendix 6](#). Physical examinations include general appearance, head, eyes,

ears, nose, and throat, neck (including thyroid and nodes), cardiovascular, respiratory, gastrointestinal, renal, neurological, musculoskeletal, skin, and others.

Height, weight, and body mass index will be assessed at screening.

8. SAMPLE SIZE AND DATA ANALYSIS

8.1. Determination of Sample Size

Approximately 68 healthy subjects (at least 30% for each sex) will be randomized into 2 groups (Group 1 and 2) with 34 subjects in each. Group 2 consists of 2 sub-groups (Group 2A and 2B) and each sub-group will be randomized with 17 subjects.

Sample Size for Primary Analysis:

A sample size of 28 evaluable subjects per treatment group will provide more than 94.4% power to exclude that CBP-307 causes more than 10-msec QTc effect at clinically relevant plasma levels, as shown by the upper bound of the 2-sided 90% confidence interval (CI) of the model-predicted QT effect ($\Delta\Delta QTcF$) at the observed geometric mean C_{max} of CBP-307 in the study. This power is estimated approximately using a 2-sample t-test. The calculation assumes a 1-sided 5% significance level, an underlying effect of CBP-307 of 3 msec and a standard deviation (SD) of the $\Delta QTcF$ of 8 msec for both CBP-307 and placebo treatment groups. Note that this calculation is conservative, since it does not take into account any gain in precision due to the use of all data of each subject with the help of a linear mixed-effects model. The concentration-QTc analysis method is supported by Darpo et al 2015³ and Ferber et al, 2015,⁴ and consistent with the experiences from 25 recent TQT studies.

Sample Size Considerations for Assay Sensitivity:

To demonstrate assay sensitivity with concentration-QTc analysis, it has to be shown that the $\Delta\Delta QTcF$ of a single dose of 400 mg moxifloxacin exceeds 5 msec (ie, the lower bound of the 2-sided 90% CI of the predicted QTc effect [$\Delta\Delta QTcF$] should exceed 5 msec). In a similarly designed, recent crossover study with 24 healthy subjects (on-file data, ERT), the standard error (SE) for the prediction of the QT effect of moxifloxacin based on the exposure-response analysis was 1.24 msec. The within-subject SD of $\Delta QTcF$ in the referred study was 5.4 msec based on the by-timepoint analysis. If the effect of moxifloxacin is assumed to be 10 msec, the SE of 1.24 msec corresponds to an effect size of $(10-5)/(1.24 \times \sqrt{24}) = 0.82$, where the effect size is the effect assumed under the alternative hypothesis divided by the SD of the test variable. This value should be compared to the effect size of 0.64 required to guarantee a power of at least 95% in a paired t-test situation with a sample size of 28 evaluable subjects. In other words, based on this calculation, a power of at least 95% will be obtained as long as the variability of the $\Delta QTcF$, as measured by its within-subject SD from the by-timepoint analysis, does not exceed 6.9 msec (ie, 128% [= 0.82/0.64] of the 5.4 msec observed in the referred study assuming the ratio of effective sizes is consistent with inverse ratio of within-subject SD). The number also agrees with recent recommendations of the FDA, which propose at least 20 subjects.⁵

8.2. Analysis Populations

8.2.1. Cardiodynamic Population

The QT/QTc population will include all subjects in the safety population with measurements at baseline as well as on-treatment with at least 1 postdose timepoint with a valid Δ QTcF value. The QT/QTc population will be used for the by-timepoint and categorical analyses of the cardiodynamic ECG parameters.

The PK/QTc population will include all subjects who are in both the QT/QTc and PK populations with at least 1 pair of postdose PK and Δ QTcF data from the same timepoint as well as subjects in the QT/QTc population who received placebo. The PK/QTc population will be used for the concentration-QTc analysis and assay sensitivity. PK/QTc population will be defined for CBP-307, and for moxifloxacin.

The as-treated principle will be applied to all analysis populations mentioned below.

8.2.2. Pharmacokinetic Population

The PK population will include all subjects who received at least 1 dose of investigational product and have evaluable PK data of any of the analytes (CBP-307 and moxifloxacin). A subject will be excluded from the PK summary statistics and statistical analysis if the subject has an AE of vomiting that occurs at or before 2 times median time to maximum concentration.

8.2.3. Safety Population

The safety population will include all subjects who received at least 1 dose of investigational product drug (therapeutic and supratherapeutic doses of CBP-307, moxifloxacin, or placebo).

For the assessment of the ECG effect of CBP-307 versus placebo, the time term incorporated into the models (both by-timepoint analysis and concentration-QTc analysis [or assay sensitivity]) includes the single predose timepoint and all postdose timepoints on Days 1, 6, and 15, and Days 1 and 16 for active versus placebo and moxifloxacin versus placebo, respectively. All times are relative to the time of dosing on that day which is considered the first dose for the assay sensitivity analysis. For the analysis of CBP-307 versus placebo, the first dose of study treatment is on Day 1.

The geometric mean of the individual C_{max} values for CBP-307 concentrations for subjects in the active drug groups on each of Days 6 and 15 will be determined, respectively. The predicted effect and its 2-sided 90% CI for placebo-corrected change-from-baseline QTcF ($\Delta\Delta QTcF$) (ie, slope estimate \times concentration + treatment effect-specific intercept) at this geometric mean C_{max} will be obtained.

To evaluate the adequacy of model fit with respect to the assumption of linearity, the observed $\Delta QTcF$ values adjusted by population time effect estimated from the model will be used. These individual placebo-adjusted $\Delta QTcF_{i,k}$ ($\Delta\Delta QTcF_{i,k}$) values equal the observed individual $\Delta QTcF_{i,k}$ for subject i administered with active drug or placebo at timepoint k minus the estimated population mean placebo effect at timepoint k (ie, time effect). A decile plot, ie, plot of the deciles of observed concentrations and the mean placebo-adjusted $\Delta QTcF$ ($\Delta\Delta QTcF$) and 90% CI at the median concentration within each decile will be given. The regression line presenting the model-predicted $\Delta\Delta QTcF$ ⁷ will be added to evaluate the fit of a linear model and visualize the concentration-response relationship. The placebo-adjusted $\Delta QTcF_{i,j}$ equals the individual $\Delta QTcF_{i,j}$ for subject i administered with CBP-307 at timepoint j minus the estimation of time at timepoint j (ie, time effect). Additional exploratory analyses (via graphical displays and/or model fitting) will include accounting for a delayed effect (hysteresis) and the justification for the choice of PD model (linear versus nonlinear) as follows.

Criteria for Negative QT Assessment

If the upper bound of the 2-sided 90% CI of the predicted QTc effect of $\Delta\Delta QTcF$ at the observed geometric mean C_{max} on Days 6 and 15 as well as clinically relevant plasma levels is below 10 msec (ie, the upper bound of the 2-sided 90% CI at the geometric mean $C_{max} < 10$ msec), it can be concluded that CBP-307 does not cause clinically concerning QT prolongation within the observed plasma concentration ranges.

Investigation of Hysteresis

Hysteresis will be assessed based on joint graphical displays of the least squares (LS) mean $\Delta\Delta QTcF$ for each postbaseline timepoint and the mean concentration of CBP-307 at the same timepoints. In addition, hysteresis plots will be given for LS mean $\Delta\Delta QTcF$ and the mean concentrations. If a QT effect ($\Delta\Delta QTcF$) > 10 msec cannot be excluded from the by-timepoint analysis in the active dose groups on Days 6 and 15; and the mean peak $\Delta\Delta QTcF$ effect is observed at the same timepoint in the by-timepoint analysis in the active dose groups on Days 6 and 15; and if the difference (delay) between the time to reach the peak QTc effect ($\Delta\Delta QTcF$) and peak plasma concentration (t_{max}) in the plot ($\Delta\Delta QTcF$ versus CBP-307) of more than 1 hour is observed in a consistent way for the active dose groups on Days 6 and 15, other concentration-QTc models, such as a model with an effect compartment, may be explored. With the provision stated above, hysteresis will be assumed if this curve shows a counterclockwise loop. A significant treatment effect-specific intercept may also be indicative of hysteresis or model misspecification, if it cannot be explained by a nonlinear relationship.

Appropriateness of a Linear Model

To assess the appropriateness of a linear model, normal quantile-quantile plots for the standardized residuals and the random effects, scatter plots of standardized residuals versus concentration and versus fitted values, and box plots of standardized residuals versus nominal time and versus active treatment will be produced. The scatter plot of standardized residuals versus concentration by locally estimated scatterplot smoothing (LOESS) fitting (ie, locally weighted scatterplot smoothing⁸ lines) also will be produced with an optimal smoothing parameter selected by the Akaike information criterion with a correction.⁹ In addition, a scatter plot of observed concentration and $\Delta QTcF$ with a LOESS smooth line with 90% CI and a linear regression line will also be provided to check the assumption of a linear concentration-QTc relationship. If there is an indication that a linear model is inappropriate, additional models may be fitted, such as an E-max model. The concentration-QTc analysis will then be repeated for the model found to best accommodate the nonlinearity detected.

Assay Sensitivity

Assay sensitivity will be demonstrated by similar concentration-QTc analysis of moxifloxacin data. If the slope of the concentration-QTc (change-from-baseline QTcF) for moxifloxacin is statistically significant at 10% level for 2-sided test and the lower bound of the 2-sided 90% CI of the predicted effect is above 5 msec at the observed geometric mean C_{max} of the 400-mg dose, assay sensitivity will be deemed to have been demonstrated.

By-Timepoint Analysis

The analysis for QTcF for CBP-307 versus placebo will be based on a linear mixed-effects model with change-from-baseline QTcF (Δ QTcF) as the dependent variable, time (ie, postbaseline timepoints on Days 1, 6, and 15: categorical), treatment (therapeutic dose of CBP-307 and supratherapeutic dose of CBP-307 on Day 15, and corresponding placebo), and time-by-treatment interaction as fixed effects. Baseline QTcF will be included in this model as an additional covariate. If necessary, a sensitivity analysis will be performed using the model without this term. An unstructured covariance matrix will be specified for the repeated measures at postdose timepoints within subjects. If the model with unstructured covariance matrix fails to converge, other covariance matrices such as compound symmetry and autoregressive will be considered. From this analysis, the LS mean, SE, and 2-sided 90% CIs will be calculated for the contrast “CBP-307 versus placebo” for each day of Days 1, 6, and 15 at each postbaseline timepoint on Days 1, 6, and Day 15, respectively.

The by-timepoint analysis for QTcF will be also performed for moxifloxacin versus placebo at postbaseline timepoints on Day 1 and Day 16. A linear mixed-effects model will be used with Δ QTcF as the dependent variable and time (ie, postbaseline timepoints on Days 1 and 16: categorical), treatment (moxifloxacin and placebo), period (as described in baseline definition for assay sensitivity), sequence (placebo/moxifloxacin or moxifloxacin/placebo), and time-by-treatment interaction as fixed effects. Baseline QTcF will be included in this model as an additional covariate. If necessary, a sensitivity analysis will be performed using the model without this term. An unstructured covariance matrix will be specified for the repeated measures at postbaseline timepoints for subject within visit. The model will also include a subject-specific random effect. If the model with an unstructured covariance matrix fails to converge, other covariance matrices, such as compound symmetry or autoregressive, will be considered. From this analysis, the LS mean, SE, and 2-sided 90% CIs will be calculated for the contrast “moxifloxacin versus placebo” at each postbaseline timepoint on Day 1, respectively.

For HR, PR, and QRS intervals, the analysis will be based on the change-from-baseline postdose (Δ HR, Δ PR, Δ QRS). The same (by-timepoint analysis) model will be used as described for QTcF. The LS mean, SE, and 90% CI from the statistical modeling for both change-from-baseline and placebo-corrected change-from-baseline values will be listed in the tables and graphically displayed.

Categorical Analyses

The analysis results for categorical outliers, T-wave morphology, and U-wave presence will be summarized in frequency tables with counts (percentages) for both the number of subjects and the number of timepoints. For categorical outliers, the number (percentage) of subjects as well as timepoints who had increases in absolute QTcF values >450 and ≤ 480 msec, >480 and ≤ 500 msec, or >500 msec, and changes from predose baseline of >30 and ≤ 60 msec, or >60 msec; increase in PR from predose baseline $>25\%$ to a PR > 200 msec; increase in QRS from predose baseline $>25\%$ to a QRS >120 msec; decrease in HR from predose baseline $>25\%$ to an HR <50 bpm; and increase in HR from predose baseline $>25\%$ to an HR >100 bpm will be determined. For T-wave morphology and U-wave presence, the analyses will be focused on change from baseline (ie, treatment-emergent changes).

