2. OBJECTIVES AND ENDPOINTS

2.1. Objectives

The primary objective of the study is:

- To evaluate the effects of therapeutic and supratherapeutic CBP-307 plasma concentrations on the heart-rate corrected QT interval (QTc) in healthy subjects.

The secondary objectives of the study are:

- To demonstrate assay sensitivity of the study to detect a small QT effect using moxifloxacin as a positive control.
- To evaluate the safety and tolerability of therapeutic and supratherapeutic multiple oral doses of CBP-307 in healthy subjects.
- To assess the PK of CBP-307 following administration of therapeutic and supratherapeutic multiple oral doses in healthy subjects.
- To evaluate the effects of therapeutic and supratherapeutic multiple oral doses of CBP-307 on HR, PR and QRS intervals, and T-wave morphology.

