3. INVESTIGATIONAL PLAN

3.1. Overall Study Design and Plan

This will be a Phase I, randomized, double-blind, double-dummy, placebo-controlled, positive-controlled, multi-site, 3-arm study to investigate the effects of therapeutic and supratherapeutic oral doses of CBP-307 on the QTc interval in healthy male and female subjects.

Potential subjects will be asked to read and sign an informed consent form (ICF). After informed consent is obtained, screening procedures and tests to establish subject eligibility to enter the study will be performed within 28 days before Day 1. After informed consent has been obtained but prior to the initiation of study treatment administration, only SAEs will be reported. After placebo administration to all subjects on Day -1, all AEs, whether

volunteered, elicited, or noted upon physical examination, will be recorded throughout the study (ie, from Day -1 until the end of the study).

In this study, approximately 68 healthy subjects (at least 30% for each sex) will be randomized into 2 groups (Group 1 and 2) with 34 subjects in each. Group 2 consists of 2 sub-groups (Group 2A and 2B) and each sub-group will be randomized with 17 subjects. Randomized subjects will receive the assigned study drug as a single dose in the morning on Days 1, 2, 3 to 6, 7 to 15, and on Day 16 (placebo will be administered to all subjects on Day -1).

[figure not shown]
The following treatments will be administered:

- Starting doses of CBP-307 for titration (0.05 mg on Day 1 followed by an up-titrated dose of 0.1 mg on Day 2)
- A therapeutic dose of CBP-307 (0.2 mg, Days 3 to 6)
- A supratherapeutic dose of CBP-307 (0.5 mg, Days 7 to 15)
- Placebo (matched to moxifloxacin and CBP-307)
- Moxifloxacin (400 mg)

Moxifloxacin will be used as a positive control to determine the assay sensitivity of this study with an expected peak QT effect (placebo-corrected change-from-baseline QTcF; $\Delta\Delta\text{QTcF}$) of 10 to 15 msec.

An overview of the study design is shown in [Figure 1](#).

Figure 1: Study Schematic

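### The criterion for a negative QT conclusion rests on the CBP-307 upper bound alone and is not tied to assay sensitivity, so as written it can be met in a study whose positive control failed

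*Protocol*

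**What the plan says.** Section 8.3, under Criteria for Negative QT Assessment, gives one condition. It opens "If the upper bound of the 2-sided 90% CI of the predicted QTc effect of" the placebo-corrected change in QTcF, requires that bound to be below 10 msec at the geometric mean Cmax on Days 6 and 15 and at clinically relevant levels, and ends "it can be concluded that CBP-307 does not cause clinically concerning QT prolongation within the observed plasma concentration ranges".

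Later in section 8.3, the Assay Sensitivity paragraph sets a two-part test for moxifloxacin. The slope must be significant at the two-sided 10% level. The second part reads: "lower bound of the 2-sided 90% CI of the predicted effect is above 5 msec at the observed geometric mean C_{max} of the 400-mg dose". If both hold, "assay sensitivity will be deemed to have been demonstrated". The paragraph stops there.

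Section 2.1 lists the matter as a secondary objective: "To demonstrate assay sensitivity of the study to detect a small QT effect using moxifloxacin as a positive control". Section 3.1 gives the purpose of the arm: "Moxifloxacin will be used as a positive control to determine the assay sensitivity of this study". Section 8.1 powers the two tests separately. For CBP-307 it states: "A sample size of 28 evaluable subjects per treatment group will provide more than 94.4% power".

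The synopsis, the objectives, the design section, section 8.1 and section 8.3 contain no sentence that makes the CBP-307 conclusion depend on the moxifloxacin result.

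**The concern.** The trial sets out to show that an effect is absent. A small CBP-307 estimate can arise because the drug does little, or because the study does not register QT effects at full size. The positive control is in the design to separate these two explanations, but the criterion does not use it.

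The protocol writes out both rules in full, with thresholds and conclusions, so this is not a detail left to the statistical analysis plan. What is fixed badly is the missing link between them. If moxifloxacin misses its bound, nothing says beforehand what that means for CBP-307, and the reading would be chosen after the data are seen.

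**Working it through.** **Inputs, all from section 8.1 unless noted.** 28 evaluable subjects per group; SD 8 msec; true CBP-307 effect 3 msec; margin 10 msec; one-sided 5%. For moxifloxacin: effect 10 msec, threshold 5 msec, reference SE 1.24 msec with 24 subjects, required effect size 0.64 at n = 28. Section 1.3 gives a mean moxifloxacin increase of 6 ms.

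**1. The plan's own figures.**
- CBP-307 criterion: SE = 8 × √(2/28) = 2.14 msec; noncentrality (10 − 3)/2.14 = 3.27; 54 df; critical t 1.674. Power by noncentral t = **94.4%**, as stated.
- Reference effect size: (10 − 5)/(1.24 × √24) = 5/6.07 = 0.82, as stated.
- Assay sensitivity at effect size 0.64: noncentrality 0.64 × √28 = 3.39; 27 df; critical t 1.703. Power = **95.1%**, matching the stated 95%.
- Assay sensitivity at the reference SE rescaled to 28 subjects: 1.24 × √(24/28) = 1.15 msec. Power = **99.5%**.

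**2. Criterion met while moxifloxacin fails, under the planning assumptions.** The tests are treated as independent.
- Reference SE: 0.9438 × (1 − 0.9953) = **0.4%**.
- Effect size 0.64: 0.9438 × (1 − 0.9510) = **4.6%**.

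**3. A study that under-registers QT effects.** Assume, for illustration only, that both drugs' effects are registered at half size with the SE unchanged.
- A true 10 msec CBP-307 effect appears as 5 msec: noncentrality (10 − 5)/2.14 = 2.34. The criterion is met in **75%** of studies, against 5% when the effect is fully registered.
- A 10 msec moxifloxacin effect appears as 5 msec, exactly at the threshold, so assay sensitivity is shown in 5%.
- Requiring both: 0.747 × 0.05 = 3.7%, or about **4%**.

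**4. Joint power if both are required.** CBP-307 power 0.9438 times assay power. The lower figure in each range uses a test-variable SD of 5/0.64 = 7.81 msec and the higher uses 6.07 msec.

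| Moxifloxacin effect | Assay power | Joint power |
|---|---|---|
| 10 msec | 95.1% to 99.5% | 89.8% to 93.9% |
| 8 msec | 63% to 82% | 60% to 77% |
| 6 msec | 16% to 21% | 15% to 20% |

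**Limits of the model.** It treats one CBP-307 comparison, although the criterion names Days 6 and 15. It leaves out the slope condition for moxifloxacin. Independence is approximate, because Groups 2A and 2B supply both the placebo and the moxifloxacin data.

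**The case against.** The criterion says what can be concluded, which is permissive. The trial is titled positive-controlled, and section 8.1 sets out what must be shown for assay sensitivity and powers it. Reading a negative result in the light of that arm is clearly the intent, and an analysis plan not shown here may say how a failure is handled. This stands in part. A reader might infer that a failed study is bound to conclude that there is no concern; the documents do not say so. They permit that conclusion and are silent on failure.

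A reader might also infer that false negative conclusions are frequent. The 75% figure does not support that. It comes from an attenuation that no section suggests, applied equally to two comparisons that are built differently: CBP-307 is a parallel comparison against a Day -1 baseline, moxifloxacin a within-subject one with other baselines. Under the plan's own assumptions the two rules part company in 0.4% to 4.6% of studies.

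Nor does the criterion favour insensitive studies in general. If the insensitivity is noise, it becomes harder to meet: at a true 3 msec, power falls from 94.4% at SD 8 to 69.5% at SD 12 and 48.9% at SD 16 (illustrative SDs), and at a true 10 msec it stays at 5%. The exposure is to attenuation, not to imprecision.

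Finally, moxifloxacin could miss its bound for reasons that leave the CBP-307 comparison intact, since its baselines are taken on other days. That argues against an absolute bar on any negative interpretation. It does not argue against stating the condition.

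**Conclusion.** The point holds as a badly fixed decision rule. Section 8.3 gives a complete sufficient condition for the trial's main conclusion that leaves out the control included to support it, and no other section supplies the link.

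The practical size is small if the planning assumptions hold and potentially large if QT effects are under-registered; how likely that is cannot be judged from the protocol. The stated powers are correct for what they cover, but 94.4% is not the power of a conclusion that also relies on assay sensitivity. The gap in the text does not depend on the attenuation illustration.

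**What to change.** In section 8.3, open the negative criterion with the condition that assay sensitivity has been demonstrated as defined in the Assay Sensitivity paragraph. Add that, if it has not, the CBP-307 estimate and its bound are still reported, but this criterion alone does not support a negative QT conclusion.

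In section 8.1, say that 94.4% is the power for the CBP-307 criterion alone, and give the approximate joint power for a 10 msec moxifloxacin effect: 93.9% at the reference SE and 89.8% at effect size 0.64.

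The cost is a few sentences, with no added subjects, data or procedures. The downside is lower power for the full claim, and it depends on the moxifloxacin effect. Section 3.1 expects a peak of 10 to 15 msec, while section 1.3 quotes a 6 ms mean. Joint power would be about 60% to 77% at 8 msec and 15% to 20% if the effect at Cmax were only 6 msec. Section 8.1 should show that range.
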